## 2 Study Objectives

### 2.1 Primary Objectives

- 1) To demonstrate the non-inferiority of the hSBA vaccine seroresponsea to meningococcal serogroups A, C, Y, and W following the administration of a 4-dose series of MenACYW conjugate vaccine compared to a 4-dose series of MENVEO® when given concomitantly with routine pediatric vaccines to infants and toddlers 6 weeks old to 15 months old.
- 2) To demonstrate the non-inferiority of the hSBA antibody response to meningococcal serogroups A, C, Y, and W following the administration of 3 doses in infancy of MenACYW conjugate vaccine compared to 3 doses in infancy of MENVEO® when given concomitantly with routine pediatric vaccines to infants at 2, 4, and 6 months of age.

The endpoints for the primary objectives are presented in [Section 9.1](#).

ahSBA vaccine seroresponse for serogroups A, C, Y, and W is defined as:

- For a subject with a pre-vaccination titer < 1:8, the post-vaccination titer must be  $\geq 1:16$
- For a subject with a pre-vaccination titer  $\geq 1:8$ , the post-vaccination titer must be  $\geq 4$ -fold greater than the pre-vaccination titer

## 2.2 Secondary Objective

- 1) To demonstrate the non-inferiority of immune responses of the routine pediatric vaccines administered concomitantly with MenACYW conjugate vaccine as compared with MENVEO® in infants and toddlers 6 weeks old to 18 months old.
- 2) To assess the antibody responses against meningococcal serogroups A, C, Y, and W after the administration of the 4th dose of MenACYW conjugate vaccine or MENVEO® when both are given concomitantly with routine pediatric vaccines at 12 months of age.
- 3) To assess the persistence of bactericidal antibodies at 12 months of age in subjects who previously received 3 doses of MenACYW conjugate vaccine or MENVEO® in infancy concomitantly with routine pediatric vaccines at 2, 4, and 6 months of age.
- 4) To describe the antibody responses against the antigens of the routine pediatric vaccines (Pentacel®, Prevnar 13®, M-M-R® II, VARIVAX®, RotaTeq®, and ENGERIX-B®) when administered concomitantly with either MenACYW conjugate vaccine or MENVEO®.
- 5) To describe the antibody responses against meningococcal serogroups A, C, Y, and W when MenACYW conjugate vaccine versus (vs) MENVEO® is administered concomitantly with routine pediatric vaccines.
- 6) To describe the antibody responses against meningococcal serogroups A, C, Y, and W when MenACYW conjugate vaccine is administered to children 12 to 15 months of age vs when MenACYW conjugate vaccine is administered to children 15 to 18 months of age, concomitantly with routine pediatric vaccines (Subgroup 1a vs Subgroup 1b), including the bactericidal antibodies persistence and the effect of 4th dose of MenACYW conjugate vaccine at 12 to 15 months of age or 15 to 18 months of age.

The endpoints for the secondary objective are presented in [Section 9.2](#).

## 2.3 Observational Objectives

### *Safety*

To describe the safety profile of MenACYW conjugate vaccine and MENVEO® when administered concomitantly with routine pediatric vaccines in healthy infants and toddlers.

The endpoints for the observational objectives are presented in [Section 9.3](#)

## 3 Investigators and Trial Organization

This trial will be conducted in approximately 60 centers in the United States. The Principal Investigators and any sub-investigators at the individual sites will be coordinated by 1 Coordinating Investigator. Details of the trial centers, the Investigators at each center, and the Coordinating Investigator are provided in the “List of Investigators and Centers Involved in the Trial” document.

An internal safety management team (SMT) will review the data being generated from all the ongoing studies with MenACYW conjugate vaccine at regular intervals for any new safety signals or safety concerns.

The Sponsor's Responsible Medical Officer (the RMO, the person authorized to sign this protocol and any amendments on behalf of the Sponsor) is [REDACTED]

## 4 Independent Ethics Committee / Institutional Review Board

Before the investigational product can be shipped to the investigational site and before the inclusion of the first subject, this protocol, the informed consent form (ICF), subject recruitment procedures, and any other written information to be provided to subjects must be approved by, and / or receive favorable opinion from the appropriate Independent Ethics Committee (IEC) or Institutional Review Board (IRB).

In accordance with Good Clinical Practice (GCP) and local regulations, each Investigator and / or the Sponsor are responsible for obtaining this approval and / or favorable opinion before the start of the study. If the protocol is subsequently amended, approval must be re-obtained for each substantial amendment. Copies of these approvals, along with information on the type, version number, and date of document, and the date of approval, must be forwarded by the Investigator to the Sponsor together with the composition of the IEC / IRB (the names and qualifications of the members attending and voting at the meetings).

The Investigator and Sponsor will submit written summaries of the status of the study to the IEC / IRB annually, or more frequently if requested. All SAEs occurring during the study that are related to vaccination will be reported by the Investigator to the IEC / IRB, according to the IEC / IRB policy.

## 5 Investigational Plan

### 5.1 Description of the Overall Study Design and Plan

#### 5.1.1 Study Design

This study is a Phase III, partially modified double-blind, randomized, parallel-group, active-controlled, multi-center study to compare the immunogenicity and safety of MenACYW conjugate vaccine and MENGEO® (Meningococcal [Groups A, C, Y, and W-135] Oligosaccharide Diphtheria CRM197 Conjugate Vaccine) when administered concomitantly with routine pediatric vaccines to healthy infants and toddlers in the US.

Approximately 2628 healthy infants aged  $\geq 42$  to  $\leq 89$  days will be randomized 2:1 to the following 2 groups:

**Group 1 (G1):** MenACYW conjugate vaccine and routine vaccines

## Group 2 (G2): MENVEO® and routine vaccines

Each group will be further randomized 2:1 in 2 subgroups based on the time of analyses conducted in the 2nd year of life (30 days after the 12-month vaccination or 30 days after the 15-month vaccination, respectively):

### Group 1:

**Subgroup 1a (G1a)** (12 months): MenACYW conjugate vaccine and routine vaccines at 2, 4, 6, and 12 to 15 months of age

**Subgroup 1b (G1b)** (15 months): MenACYW conjugate vaccine at 2, 4, 6, and 15 to 18 months of age and routine vaccines at 2, 4, 6, 12 to 15 months of age, and 15 to 18 months of age

### Group 2:

**Subgroup 2a (G2a)** (12 months): MENVEO® at 2, 4, 6, and 12 months of age and routine vaccines at 2, 4, 6, 12, and 15 to 18 months of age

**Subgroup 2b (G2b)** (15 months): MENVEO® at 2, 4, 6, and 12 months of age and routine vaccines at 2, 4, 6, 12, and 15 to 18 months of age

The schedule of vaccination and blood sampling is further detailed in [Table 5.1](#).

All subjects will receive the following routine vaccines as per the ACIP recommendations (see [Table 5.1](#)):

Pentacel® (DTaP-IPV/Hib) at 2, 4, 6, and 15 to 18a months of age

Prevnar 13® (pneumococcal 13-valent conjugate vaccine [PCV13]) at 2, 4, 6, and 12 to 15 months of age

RotaTeq® (pentavalent rotavirus vaccine [RV5]) at 2, 4, and 6 months of age

ENGERIX-B® (HB vaccine) at 2 and 6 months of ageb

M-M-R® II (measles, mumps, rubella [MMR] vaccine) at 12 to 15 months of age

VARIVAX® (varicella vaccine) at 12 to 15 months of age

In addition, subjects in Subgroup 1b and Group 2 will receive the first dose of hepatitis A (HepA) vaccine (HAVRIX®) at 15 to 18 months of age as part of the study. For Subgroup 1a, there will be no HepA vaccination provided as part of the study. Subjects in Subgroup 1a should be vaccinated, as per standard practice, after the completion of the last study visit.

Blood sample for immunogenicity assessment will be assayed for meningococcal antibodies and for antibodies elicited in response to selected routine pediatric vaccines.

a Subjects in Subgroup 1a will complete the last study visit at 13 to 16 months of age. For subjects in Subgroup 1a, the 4th dose of Pentacel® which is administered at 15 to 18 months of age, will be provided by the Sponsor for completion of the DTaP series with vaccine from the same manufacturer, as per ACIP recommendation. The study personnel / Investigator will be responsible for administering this dose at the recommended age outside of the scope of the study.

b First dose of HB vaccine must be given at least 28 days prior to study enrollment.

Safety data will be collected as follows: Immediate unsolicited systemic AEs will be collected within 30 minutes after each vaccination. Solicited-AE information will be collected from D0 to D07 after each vaccination; unsolicited-AE information will be collected from D0 to D30 after each vaccination; SAE (including adverse events of special interest [AESIs]) and medically-attended-adverse-event (MAAE) information will be collected throughout the study from Visit 1 until the end of the 6-month follow-up period after the last vaccination.

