Planned Sample Size:	
Approximately 2628 subjects are planned to be enrolled.
 
Group 1 (MenACYW conjugate and routine vaccines): n=1752
 
Subgroup 1a: n=1168 enrolled, 770 evaluable Subgroup 1b: n=584 enrolled, 385 evaluable
 
Group 2 (MENVEO® and routine vaccines): n=876
 
Subgroup 2a: n=584 enrolled, 385 evaluable Subgroup 2b: n=292 enrolled, 192 evaluable

Schedule of Study Procedures	
Vaccination
 
All subjects will receive either 4 doses of MenACYW conjugate vaccine or 4 doses of MENVEO® administered concomitantly with routine pediatric vaccines.
 
All subjects will receive the following routine pediatric vaccines as per the ACIP recommendations:
 
 
• Pentacel® (DTaP-IPV//Hib) at 2, 4, 6, and 15 to 18* months of age
 
• Prevnar13® (PCV13) at 2, 4, 6, and 12 to 15 months of age
 
• RotaTeq® (RV5) at 2, 4, and 6 months of age
 
• ENGERIX-B® (HB vaccine) at 2 and 6 months of age**
 
• M-M-R® II (MMR vaccine) at 12 to 15 months of age
 
• VARIVAX® (varicella vaccine) at 12 to 15 months of age
 
 
In addition, subjects in Subgroup 1b and Group 2 will receive the first dose of hepatitis A vaccine (HAVRIX®) at 15 to 18 months of age as part of the study. For Subgroup 1a there will

be no HepA vaccination provided as part of the study. Subjects in Subgroup 1a should be vaccinated as per standard practices after the completion of the last study visit.

\*Subjects in Subgroup 1a will complete the last study visit at 13 to 16 months of age. For subjects in Subgroup 1a, the 4th dose of Pentacel®, which is administered at 15 to 18 months of age, will be provided by the Sponsor for completion of the DTaP series with vaccine from the same manufacturer, as per ACIP recommendation. The study personnel / Investigator will be responsible for administering this dose at the recommended age outside of the scope of the study.

\*\*First dose of HB vaccine must be given at least 28 days prior to study enrollment.

Blood sampling

All subjects in the study will have 4 blood draws each. Blood collection is as follows:

- 1) Before first study vaccination at Visit (V) V01 for all subjects
- 2) 30 to 51 days (V04) after receiving the 6-month vaccinations (after 3rd dose) for all subjects
- 3) Before the 12-month vaccination (V05) for Subgroups 1a and 2a

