\*This call is made 8 days after the respective vaccinations. If day 8 falls on a weekend or holiday, the telephone call may be made on the following business day. During this telephone call, the staff will find out whether the subject experienced any SAE (including AESI) and/or MAAE not yet reported and will remind the subject's parent/guardian to continue using the diary card, to bring the diary card to the study center at the next visit, and confirm the date and time of the next visit

†Staff will contact the subjects' parent/ guardian by telephone within 14 days before V05 to remind them about the forthcoming study visit. If the subject's participation in the study is discontinued, the information recorded on the diary card will be reviewed at this time and the diary card will be retrieved by the site.

‡At V05, subjects must be between 12 and 15 months of age (from the day subjects become 12 months old until the day before becoming 16 months old).

§Staff will contact the subject's parent/ guardian by telephone at 6 months (+ 30 days) after the last vaccination visit to identify the occurrence of any SAEs (including any AESIs) and MAAEs not yet reported. The final telephone call will continue until contact is made or 28 days have passed at which time the subject will be considered lost to follow-up.

\*\*Physical examination should be done as per standard of care.

††Temperature needs to be measured before each vaccination and recorded in the source documents.

†††Should a subject receive oral or injectable antibiotic therapy within 3 days prior to any blood draw, the investigator will postpone that blood draw until it has been 3 days since the subject last received oral or injectable antibiotic therapy. Postponement must still be within the timeframe for blood draw. If postponement would result in the sample collection falling outside of this timeframe, the blood sample should be collected without postponement, and it should be documented appropriately that the sample was taken less than 3 days after stopping antibiotic treatment.

§§During the 2nd year of life study visits, if blood is collected as part of the study, additional blood can be optionally collected via the same venipuncture for screening of iron deficient anemia and/or lead level as per AAP/CDC recommendations. This collection must be done in serum tubes not provided as part of the study and as per local standard of care.

\*\*\*Blood sample will be drawn prior to vaccinations.

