**Safety Follow-up Telephone Call 6 (180 [+30] days after Visit 5): Collection of SAEs (including AESIs) and MAAEs**

- 1) Ask the parent / guardian if the subject has experienced any SAE/MAAE since the last study visit. If an SAE, including an AESI, has occurred, follow the instructions in [Section 10](#) for reporting it.
- 2) Complete the relevant CRFs for this visit.

This call must be made by a qualified person, such as a physician or qualified study nurse.

A follow-up visit outside the scope of this study protocol can be arranged depending on the information recorded during the phone calls.

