- Category 2 medications will be reported in the CRB during the study period up to the last blood draw.
- Category 3: Systemic (Oral or injectable) antibiotics, as they may interfere with bioassays used for antibody testing when taken before a blood draw. Antibiotics that the subject received within 72 hours preceding each visit for blood draw related to IMP assessment (meningococcal vaccines) and used to define the PPAS.
- Category 3 medications will be reported in the CRB for the period of 3 days (72 hours) before each blood draw.

*Note: Topical antibiotics (Inhaled, otic, ophthalmic, nasal, etc.) should not be captured or reported.*

The information reported in the CRB for each reported medication will be limited to:

- Trade name
- Rationale for the origin of prescription: Whether it was a prophylactica\* medication? Prophylactic medications will be recorded in the Action Taken section of the AE collection tables.
- Medication category (1, 2, or 3)
- Start and stop dates

Dosage and administration route, homeopathic medication, will not be recorded.

a Medication(s) prescribed for preventing AE occurrence (e.g. paracetamol to reduce the risk of fever)

If the subject has received medications other than those listed in Categories 1, 2, and 3, the detailed information will be collected in the source documents only.

Medications given to treat an AE will be captured in the “Action Taken” section of the AE CRB only. No details will be recorded in the concomitant medication CRB unless the medication(s) received belongs to one of the prelisted categories.

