4.4.2.2.3 Last Vaccination

Last vaccination before an unsolicited AE is derived from the start date of the unsolicited AE provided in the CRF and is calculated as follows:

- If an unsolicited AE has a complete start date and different to any of the vaccination dates, the start date is used to determine the last vaccination before the unsolicited AE.

- If the start date is missing or partially missing, or equal to any vaccination date, then the visit number in the “Appeared after Visit” or similar field, is used to determine the last vaccination before the unsolicited AE.

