4.4.2.3 SAEs (including AESIs)

An event will be considered as a serious event if “Yes” is checked for “Serious” in the CRF. An event will be considered as an AESI if “Yes” is checked for “Is the event an AESI?” in the CRF.

SAEs (including AESIs) will be analyzed throughout the study using the following periods:

- Within 7 days (D0 to D7) after vaccination
- Within 30 days (D0 to D30) after vaccination
- During the study (i.e., all SAEs occurred during the study), including the 6-month follow-up period
- During the 6-month follow-up

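### In Subgroup 1a the off-study fourth Pentacel dose falls inside the post-Visit 5 safety follow-up for nearly all children, and no CRB record of its date is specified, so period-specific SAE and AESI tables are not like for like across subgroups

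*Protocol*

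**What the plan says.** Protocol Sections 5.1.1 and 6.1.3.3 schedule Pentacel for all subjects at 2, 4, 6 and 15 to 18 months. For Subgroup 1a the sponsor supplies the fourth dose, but "The study personnel / Investigator will be responsible for administering this dose at the recommended age outside of the scope of the study". HepA for this subgroup is left to standard practice after the last study visit, with no age given.

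The last study vaccination in Subgroup 1a is Visit 5, allowed "from the day subjects become 12 months old until the day before becoming 16 months old". Visit 6, 30 to 51 days later, is the last visit and the last blood draw. Section 5.1.4.2 then sets "Safety Follow-up Telephone Call 6 (180 [+30] days after Visit 5): Collection of SAEs (including AESIs) and MAAEs". The Synopsis gives "Subgroup 1a: n=1168 enrolled, 770 evaluable".

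On recording, Protocol Section 6.6 limits Category 2 vaccines to those not described in the protocol and given within 28 days of a trial vaccination, and adds: "Category 2 medications will be reported in the CRB during the study period up to the last blood draw". Medications outside the three categories stay in source documents.

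On analysis, SAP Section 4.4.2.2.3 says that when an event has a complete start date that is not itself a vaccination date, "the start date is used to determine the last vaccination before the unsolicited AE". SAP Section 4.4.2.3 tabulates SAEs and AESIs within 7 days, within 30 days, over the whole study, and "During the 6-month follow-up". SAP Section 4.4.2.4 gives MAAEs only the first three of these periods.

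In Subgroups 1b, 2a and 2b, Pentacel with HAVRIX at 15 to 18 months is a study vaccination visit. It has its own D0 to D30 collection, and the six-month call is counted from it.

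**The concern.** The same routine vaccine is treated in two ways. In 1b and in all of Group 2, an SAE or AESI in the month after the fourth Pentacel dose belongs to a study vaccination window, and the six-month follow-up starts after that. In 1a, the same event has no vaccination to be tied to except Visit 5, and it lands in the six-month follow-up period.

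Subgroup 1a is two-thirds of the MenACYW group, so a side-by-side reading of the follow-up tables compares a period that contains an unmarked DTaP-IPV/Hib dose in most of Group 1 with a period that contains none by design in Group 2. The AESIs include febrile and non-febrile generalized seizures, for which time since the latest vaccine is what a safety reader wants to know. The protocol (Section 1.4) also says this trial will contribute significantly to the US safety database.

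**Working it through.** **Inputs.** Visit 5 in 1a at 12.0 to <16.0 months; follow-up to Visit 5 + 180 (+30) days; Pentacel at 15 to 18 months, read as 15.0 to <19.0 months because the protocol reads the 1b Visit 6 window that way; earliest stated opportunity for routine vaccines outside the study is Visit 6, at least 30 days after Visit 5. One month = 30.44 days, so 180 days = 5.91 months and 210 days = 6.90 months.

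**The plan's own figures.** The 1a schedule states a final contact at 18 to 21 months and a duration of 16 to 19 months. Visit 5 at 12 or 15 months gives 12 + 5.91 = 17.91 and 15 + 5.91 = 20.91 months; less 2 months at entry, 15.91 and 18.91. Both reproduce.

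**Size of the subgroup.** 1168/1752 = 66.7% of Group 1; 1168/2628 = 44.4% of the trial.

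**Share of the Pentacel window inside follow-up.** For Visit 5 at age a, up to about 14 months, the share is (a + follow-up − 15)/(19 − 15), capped at 100%. For later Visit 5 ages the window opens at Visit 6 and the share is 100%.

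| Visit 5 age (months) | to day 180 | to day 210 |
|---|---|---|
| 12.0 | 73% | 98% |
| 12.5 | 85% | 100% |
| 13.0 | 98% | 100% |
| 13.1 and above | 100% | 100% |

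The share reaches 100% from a = 19 − 5.91 = 13.09 months (day 180) or 19 − 6.90 = 12.10 months (day 210).

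**Averaging over children.** The documents give no age distribution, so I assume uniform ages within each window.
- All Visit 5 ages at 12 to <13 months: average share to day 180 = (12.5 + 5.91 − 15)/4 = 85%.
- Visit 5 ages spread over 12 to <16 months: average shortfall = (1.086² / 2 / 4) / 4 = 3.7%, so 96%.
- To day 210 the shortfalls are 0.1% or less in the first case (0.10² / 8 = 0.13% before rounding) and 0.03% in the second, so more than 99% in both.
- If the dose is given at the earliest permitted time, it is inside for every child, with about 89 to 150 days of follow-up left to day 180.

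**Routes by which the date could reach the analysis database.**
- The 1a schedule has no vaccination entry after Visit 5, and its concomitant-medication row ends at Visit 6.
- Category 2 does not fit: Pentacel is described in the protocol, the dose is normally well beyond 28 days after Visit 5, and reporting ends at the last blood draw.
- Telephone Call 6 and the memory aid cover SAEs (including AESIs) and MAAEs only.
- Product accountability (Protocol Section 6.2.2.3) requires records of doses given to each subject, with label information in source and CRB. It mentions neither an administration date nor this dose.

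**Consequence.** With no date, the rule in SAP Section 4.4.2.2.3 returns Visit 5 for any later event in 1a. The SAP has no cut or flag at the off-study dose.

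**The case against.** The design is disclosed openly in several places, and routine vaccination during long-term infant follow-up is expected. Safety is descriptive with no hypotheses, so no formal conclusion turns on these tables. If anything, extra events after a licensed vaccine would add to the investigational group's follow-up count. These points stand and limit the weight of the finding, but they do not make the tables comparable.

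Causality is judged case by case, SAEs get a second sponsor assessment, and the same site gives the dose. From 22APR2020 the database also holds relationship to non-IMP vaccines (SAP Section 5.4.1.2). This is a partial mitigation. It began two years after the planned start of 25 April 2018, the SAP does not say that it covers an out-of-scope dose, and causality does not supply timing.

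Four stronger readings are tempting and not supported:
- That every 1a child has the dose inside follow-up. A child with Visit 5 near 12 months and Pentacel late in the window could receive it after the call.
- That the date is not collected in the CRB. No text says so. Accountability leaves it open, and SAP Section 5.8 reports that the concomitant-medication category fields were inactivated, which weakens any argument resting on Category 2 alone. What can be said is that no collection is specified.
- That later events are attributed to MenACYW dose 4. The rule points to Visit 5, which also includes PCV13, M-M-R II and VARIVAX, and a time period is not a causal judgement.
- That a count of MAAEs contaminates the follow-up table. The SAP plans no separate six-month period for MAAEs, and the documents give no event rates from which to project one.

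**Conclusion.** The point holds as a gap in recording and tabulation. Nearly all of the 1168 children enrolled in Subgroup 1a are due a sponsor-supplied, site-administered Pentacel dose during their follow-up after Visit 5: about 85% to 96% by day 180 and more than 99% by day 210. These figures rest on uniform ages at Visit 5 and at the dose, and they ignore dropout.

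The effect is confined to the period-specific SAE and AESI tables and to the timing of MAAEs relative to vaccination. Whole-study totals are largely unaffected, because the dose falls on study in 1b, 2a and 2b and inside follow-up for most of 1a. How many SAEs or AESIs are involved cannot be estimated from the documents. Whether any HepA dose also falls in the period depends on local practice. Immunogenicity, sample size and power are untouched.

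**What to change.** Change no dosing. State in the SAP whether the date of this Pentacel dose is held in the CRB for Subgroup 1a. If it is not, enter it from site dosing or accountability records, or at Telephone Call 6, together with the date of any HepA dose given before the call.

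In the SAP, classify 1a follow-up SAEs and AESIs as before, within D0 to D30 of, or after that date, and list MAAEs with the same flag. Alternatively, add a sensitivity summary of 1a follow-up censored at the dose. For events after the dose, do not present Visit 5 as the most recent vaccination without that flag.

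The cost is a small data-entry burden and one extra table. No additional visit or sample is needed, and the site that gives the dose should already hold the record.
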